#### Secondary Outcome(s)

1. Adult ADHD self-report scale (ASRS), the 18 items version
2. Beck Depression Inventory (BDI)
3. Beck Anxiety Inventory (BAI)
4. Alcohol Use Disorder Identification Test (AUDIT)
5. Drug Use Disorder Identification Test (DUDIT)
6. Weiss Functional Impairment Rating Scale, self-report (WIFRS)
7. Adult ADHD Quality of Life Scale (AAQoL)
8. Global Assessment of functioning (GAF)

The following parameters of *clinical treatment* recorded from patient journal:

- Type of medication, dosage, intervals, efficacy and duration.
- Diagnosis (subtype and comorbidities).

## 8. SAFETY ASSESSMENTS

The investigator is responsible for the detection and documentation of events meeting the criteria and definition of an adverse event (AE) or serious adverse event (SAE). Each patient will be instructed to contact the investigator immediately should they manifest any signs or symptoms they perceive as serious. Included patient participants will already have been evaluated by treating clinicians. The methods for collection of safety data are described below.

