**Fig. 1 Trial flow-chart**

In an uncontrolled extension phase of the initial 14 week trial, participants initially receiving TAU will be offered the DBT-based group treatment. All participants will be re-assessed at follow-up 6-months after ended DBT-bGT.

Study Period: Estimated date of first patient enrolled: December 2015  
Anticipated recruitment period: 1 years  
Estimated date of recruitment end: 31/12/2016  
Estimated date of last patient completed follow-up: 15.05.2017

Treatment Duration: The DBT-based group therapy (DBT-bGT) /structured skills training group treatment lasts for 14 weeks, and thereafter participants will be re-assessed at follow-up 6-months after. Those of the participants receiving initial TAU conditions will have an additional duration of 3 months representing the duration of treatment as usual.

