## 5. INVESTIGATIONAL INTERVENTION

### 5.1. Elements of the DBT-based group therapy

The structured skills group treatment uses elements from DBT such as psychoeducation, acceptance, mindfulness, and functional behavioral analysis, such targeting symptoms and functional problems common in ADHD. It consists of 14 weekly group sessions, each lasting two hours separated by a 15-minute break. Each group includes 7-9 patients with ADHD and two therapists. Group sessions follow a structure with manualized instruction for the therapists and workbook for the patients.

A typical session begins with introducing a new mindfulness exercise performed together in the group. The first part of the session then focuses on feedback on last week's homework of skill training, while the second part introduces a new topic and related homework for the next week. The topics for the different sessions include psychoeducation, mindfulness, functional behavioral analyses, and how to understand and manage different symptoms and aspects of ADHD, e.g. impulsivity, addiction, emotional

regulation, self-esteem, and relation to others. Interaction between the participants is important, and the therapists should encourage and balance their feedback and discussion during the session. After each group session, patients will receive 15-20 minutes of individual coaching with one of the therapists. This is an add-on element according to a Swedish adaptation of the program. The coaching focuses on adherence to homework related to each participant's situation and pre-defined goals.

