### 8.1. Definitions

#### 8.1.1. Adverse Event (AE)

An adverse event (AE) can be any unfavourable and unintended sign (including an abnormal laboratory finding), symptom, or disease temporally associated with the use of a medicinal (investigational) product, whether or not related to the medicinal (investigational) product.

This study does not delay nor administer medication as part of the study. However any untoward medical occurrence that results in any of the following will be reported:

- Results in death
- Is immediately life-threatening
- Requires in-patient hospitalization or prolongation of existing hospitalization
- Results in persistent or significant disability or incapacity
- Is a congenital abnormality or birth defect
- Is an important medical event that may jeopardize the subject or may require medical intervention to prevent one of the outcomes listed above

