### **8.2.2. Clinical Study Report**

The unexpected adverse events and serious adverse events occurring during the study will be discussed in the safety evaluation part of the Clinical Study Report.

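### Section 8 specifies no enquiry about adverse events, and the chance that an event comes to light in the 14-week randomised phase differs between the arms

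*Protocol*

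**What the plan says.** **Detection.** Section 8 places a general duty on the site: "The investigator is responsible for the detection and documentation of events meeting the criteria" of an AE or SAE. It then gives one concrete instruction: "Each patient will be instructed to contact the investigator immediately should they manifest any signs or symptoms they perceive as serious". The section closes by saying that the collection methods come next. Section 8.1.1 limits reporting to events with listed consequences, introduced by "However any untoward medical occurrence that results in any of the following will be reported". The list runs from death and hospitalisation to medical events judged important. Section 8.2.1 covers CRF entry and SAE reporting within 24 hours of the site learning of the event.

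**Contact.** Section 5.1 gives DBT-bGT patients 14 weekly group sessions and adds: "After each group session, patients will receive 15-20 minutes of individual coaching with one of the therapists". Section 5.2 leaves TAU unstandardised and variable between individuals and clinics. Section 7.1 schedules assessments before treatment, at the end of group treatment or 14 weeks of TAU, and at the 6-month follow-up.

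**Reporting.** Section 8.2.2 says: "The unexpected adverse events and serious adverse events occurring during the study will be discussed in the safety evaluation part of the Clinical Study Report". It names no phase. Under Fig. 1 in Section 4, the period after the first 14 weeks is called an uncontrolled extension, in which TAU patients are offered DBT-bGT. Those patients "will have an additional duration of 3 months representing the duration of treatment as usual".

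**Existing record source.** Under Secondary Outcome(s), medication and diagnosis are "recorded from patient journal".

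**The concern.** A safety record is only as good as the step by which an event first becomes known. Here that step is left to the patient's own view of what is serious. Everything in Section 8.2 begins after the site already knows.

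The arms also differ in how often a patient is in front of someone connected with the trial. A patient in a weekly group with individual coaching has regular occasions to mention a crisis, a hospital admission or a deterioration. A TAU patient has whatever contact the local clinic provides, and the protocol gives no route from that clinic to the investigator.

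Two things are at stake. Harms may be missed in both arms. They may also be missed more often under TAU, which would make DBT-bGT look relatively less safe than it is. An event that was never asked about cannot be recovered at the analysis stage, so this has to be settled in the protocol.

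**Working it through.** The protocol gives no safety rate, detection rate or observation-time ratio, so there is no stated figure to reproduce. The check sets the sections side by side and then works out the observation times.

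**1. Is there any enquiry about events?**

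- Section 8: investigator's duty to detect, and patient-initiated contact. No visit, question or schedule.
- Section 8.1.1: definitions and reportable consequences only.
- Section 8.2.1: recording and reporting of known events.
- Section 8.2.2: discussion in the study report.
- Section 7.1: assessments in both arms at baseline, week 14 and follow-up. No event questions are listed.
- Secondary Outcome(s): journal extraction covers medication and diagnosis, not events.
- Section 9.2: medical records should hold information important for safety, but the itemised minimum is test dates, ASRS scores and withdrawal.

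No section says when, how or by whom participants are asked about events.

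**2. Scheduled project contact between baseline and week 14**

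- DBT-bGT: 14 weekly occasions. Coaching follows directly on each session, so this is 14 occasions and not 28.
- TAU: none scheduled by the project. Usual clinical contact continues at an unstated frequency, so the true number of clinical contacts is unknown rather than zero.

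**3. Planned observation time**

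Inputs: 14 weeks of DBT-bGT; 6 months of follow-up after it, taken as 26 weeks; a preceding TAU period of 14 weeks by design, or 3 months (13 weeks) in the text under Fig. 1.

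- DBT-first: 14 + 26 = 40 weeks.
- TAU-first: 14 + 14 + 26 = 54 weeks, or 13 + 14 + 26 = 53 weeks.
- Relative excess: 54/40 − 1 = 35.0%; 53/40 − 1 = 32.5%.
- With 6 months taken as 24 weeks: 52/38 − 1 = 36.8%; 51/38 − 1 = 34.2%.
- Randomised phase only: 14/14 − 1 = 0%.

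The whole-study excess is therefore about 32% to 37%. It applies to TAU-first patients who accept DBT-bGT and complete follow-up.

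**4. What this means for counts (illustration)**

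Assumptions not in the protocol: an equal true event rate r per patient-year in both arms, 120/2 = 60 patients per arm, and complete follow-up and uptake. Expected patients with at least one event over w weeks = 60 × (1 − exp(−r × w/52.18)).

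| Assumed r | DBT-first, 40 weeks | TAU-first, 54 weeks | Ratio | Each arm, 14 weeks |
|---|---|---|---|---|
| 0.02 | 0.9 | 1.2 | 1.35 | 0.3 |
| 0.10 | 4.4 | 5.9 | 1.33 | 1.6 |
| 0.20 | 8.5 | 11.2 | 1.32 | 3.1 |

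A crude whole-study count would differ by about a third at equal rates. In the 14-week phase the time imbalance vanishes. Expected numbers there are small over this range, so even one or two undetected events would matter. The detection imbalance in step 2 remains, and the protocol gives nothing from which to size it.

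**The case against.** The strongest reply is that the protocol plans no comparison of safety between the arms. Safety is not among the objectives or outcomes, and Section 8.2.2 promises only a discussion of events. That section sets the scope of reporting; it does not prescribe a pooled count by randomised arm. Tabulation by phase or by person-time is commonly left to a SAP, which is not shown. All of this stands, and the 40 against 53 to 54 weeks is therefore not an error in the protocol.

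A reader might go further and infer that safety cannot be compared by arm at all, or that unequal detection and unequal time are inseparable. The document does not support either. Both arms share the same 14 weeks, and restricting to that window removes the time imbalance.

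Other points against the concern:

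- The investigator is responsible for detection in both arms, both arms are assessed at week 14, and the instruction to patients is the same. True, but a duty without a procedure is not an enquiry.
- No section tells group therapists to ask about or report events, and coaching is directed at homework. Greater detection under DBT-bGT is thus an inference from opportunity, not a documented fact.
- Deaths and hospitalisations depend less on contact frequency than minor complaints do. This stands and narrows the concern, although medical events judged important still depend on someone hearing of them.
- TAU patients may see their own clinicians. They may, but neither the frequency nor a route to the investigator is fixed.

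The missing enquiry survives these points. A SAP can decide how to tabulate events, but it cannot supply events that were never collected.

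**Conclusion.** The concern holds for how events are found. Section 8 promises collection methods and gives none beyond patient-initiated contact, and scheduled contact with therapists in the randomised phase is 14 occasions under DBT-bGT against none fixed under TAU. Following the plan as written risks under-detection of harms, with unequal opportunity by arm.

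The size of any bias cannot be computed from the protocol. Any specific inflation factor would be no more than the ratio of two assumed detection rates. The direction, more events noticed under DBT-bGT, rests on the assumption that regular contact brings events to light.

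The difference in whole-study observation, about 32% to 37%, is a caution for any by-arm display that runs past week 14. It assumes full uptake of the delayed treatment and complete follow-up.

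**What to change.** In Section 8, state one short set of fixed event questions, put to every participant in both arms at the existing week-14 and follow-up assessments, with event dates recorded. Add hospitalisations, self-harm and deaths to the journal extraction already planned under Secondary Outcome(s), over the same window in each arm. Record the source of each event, so that any comparison can rest on sources common to both arms.

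In Section 8.2.2, add that if events are shown by arm, the 14-week randomised phase is shown separately from the uncontrolled extension.

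The cost is a few minutes of site time at each existing visit and a few more journal fields. No visit is added, and no treatment or clinical rule changes.

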### 8.1. Definitions

#### 8.1.1. Adverse Event (AE)

An adverse event (AE) can be any unfavourable and unintended sign (including an abnormal laboratory finding), symptom, or disease temporally associated with the use of a medicinal (investigational) product, whether or not related to the medicinal (investigational) product.

This study does not delay nor administer medication as part of the study. However any untoward medical occurrence that results in any of the following will be reported:

- Results in death
- Is immediately life-threatening
- Requires in-patient hospitalization or prolongation of existing hospitalization
- Results in persistent or significant disability or incapacity
- Is a congenital abnormality or birth defect
- Is an important medical event that may jeopardize the subject or may require medical intervention to prevent one of the outcomes listed above

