## **8.2. Procedure**

### **8.2.1. AEs and SAEs**

All adverse events and serious adverse events that should be reported as defined in section 8.1.1 will be recorded in the patient's CRF.

The investigator must report SAEs to the sponsor, within 24 hours after the site has gained knowledge of the SAE. The investigator must document every SAE on the CRF. The Serious Adverse Event Report Form must be completed, signed and sent to sponsor 1. The initial report shall promptly be followed by detailed, written reports if necessary. The initial and follow-up reports shall identify the trial subjects by unique code numbers assigned to the latter.

The sponsor 1 keeps detailed records of all SAEs reported by the investigators and performs an evaluation with respect to seriousness, causality and expectedness.

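### Section 8.1.1 ties adverse events to a medicinal product the trial does not give and limits reporting to serious outcomes, so non-serious harms of the group therapy that no scale measures have no capture rule

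*Protocol*

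**What the plan says.** Section 8.1.1 of the protocol takes its definition from drug trials: an adverse event is an unfavourable sign, symptom or disease "temporally associated with the use of a medicinal (investigational) product, whether or not related to the medicinal (investigational) product". The next paragraph states "This study does not delay nor administer medication as part of the study" and continues "However any untoward medical occurrence that results in any of the following will be reported". Six outcomes follow: death, immediate threat to life, hospitalisation, lasting disability, birth defect, and an important medical event.

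Section 8.2.1 sets what goes on the case report form by referring back: "All adverse events and serious adverse events that should be reported as defined in section 8.1.1 will be recorded in the patient's CRF". Section 8 makes the investigator responsible for detecting and documenting "events meeting the criteria and definition of an adverse event (AE) or serious adverse event (SAE"), and says of participants: "Each patient will be instructed to contact the investigator immediately should they manifest any signs or symptoms they perceive as serious". Section 8.2.2 says what the study report will cover: "The unexpected adverse events and serious adverse events occurring during the study will be discussed".

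**The concern.** The definition depends on an exposure that is not part of the trial, and the operative reporting rule covers only serious outcomes. The surrounding sections still speak of adverse events and serious adverse events as two kinds of record. A site that follows the text has no usable rule for a non-serious event. Such events will be recorded by local habit or not at all.

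What is at stake is the harms side of the comparison of DBT-bGT with TAU. If the study report lists few or no non-serious adverse events, a reader could not tell whether there were few or whether nobody was asked to record them. A statistical analysis plan cannot repair this later, because it can only analyse what was collected.

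**Working it through.** No figure is involved, so the check sets the sections side by side.

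**1. Does the definition fit the trial?** Section 8.1.1 requires use of a medicinal (investigational) product. Section 5.1 describes the investigational intervention as 14 weekly group sessions, and section 5.2 describes the control as unstandardised usual care. Section 8.1.1 itself says the study gives no medication. Two generous readings might rescue the definition:

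- *Medicinal product means the participant's own ADHD medication.* Section 3.2.1 admits patients both on and off medication, so this covers only some participants. It also ties the event to the drug, not to the therapy under test.
- *Investigational product means the group therapy.* This gives the DBT-bGT arm a definition, but leaves the TAU arm without one in the 14 weeks that form the controlled comparison. The reporting rule in step 2 would still decide what is reported.

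**2. What must be reported and recorded?** Section 8.1.1 requires reporting of events with one of the six outcomes. Section 8.2.1 limits recording to events reportable under 8.1.1. Section 8 asks participants to make contact about what they themselves regard as serious. No section clearly requires a non-serious event to be recorded.

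**3. What do the other sections promise?** Sections 8, 8.2.1 and 8.2.2 all name adverse events alongside serious adverse events, and 8.2.2 expects unexpected adverse events to be discussed. Section 8.1 contains only 8.1.1, so the serious category has no definition of its own, although 8.2.1 attaches a 24-hour reporting duty to it. The terms also vary elsewhere: the synopsis expands SAE with the word severe, and section 6.4.1 uses a further undefined category of significant events.

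**4. Which harms are captured as the text stands?**

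| Kind of harm | Route in the protocol | Comparable between arms? |
|---|---|---|
| Event meeting one of the six criteria | 8.1.1 and 8.2.1, whichever arm | Yes |
| Worse depression, anxiety, alcohol or drug use, functioning or quality of life | BDI, BAI, AUDIT, DUDIT, Weiss scale, AAQoL and GAF at the section 7.1 assessments | Yes, as mean change |
| Harm leading to withdrawal | 6.4.1, reason recorded if disclosed | In part |
| Other non-serious harm, such as distress in the group | None | No |

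**5. Do the partial routes close the gap in the last row?** They do not, for three reasons:

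- Section 10.3 compares group means and drops participants with missing values from each analysis. Someone who worsens and leaves without completing a scale is absent from that comparison.
- Withdrawal reasons depend on disclosure.
- Reporting is initiated by the participant, and contact differs by arm. Section 5.1 gives DBT-bGT participants weekly sessions plus 15 to 20 minutes of individual coaching after each, while contact under TAU varies by patient and clinic. Opportunities to mention an event may therefore be unequal.

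**The case against.** The best defence is that section 8.1.1 opens with a generic drug-trial definition, openly says that no medication is given, and then states the rule meant for this trial: report serious outcomes. Restricting collection to serious events can be a legitimate choice for a psychotherapy trial added to ordinary care, and that rule works. It depends on neither drug nor arm, and section 8.2.1 supports it with 24-hour reporting and sponsor evaluation. Tabulation by arm can be left to a statistical analysis plan.

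Much of this stands. The serious-event rule is usable, and missing tabulations are no fault here. The defence fails on one point: the protocol does not declare a serious-only policy. Sections 8, 8.2.1 and 8.2.2 say the opposite by promising adverse events as a separate category.

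A reader might go further and infer any of three things that the protocol does not support:

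- *That harms of the therapy cannot be compared between arms at all.* Serious events are reportable in either arm, and the scales measure symptom worsening in both.
- *That the adverse event count must be zero for all 120 participants.* Some may take their own medication, so even a literal reading does not yield zero.
- *That new suicidal ideation without hospitalisation would necessarily go unrecorded.* An investigator could class it under the sixth criterion, the important medical event.

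**Conclusion.** The point holds in a limited form. The adverse event definition does not fit the trial, the serious category has no definition of its own, and the safety sections disagree on whether non-serious events are collected. The consequence is confined to non-serious harms of the group therapy that no outcome scale measures. These are not usably defined or systematically captured in either arm, so they cannot be compared as adverse events.

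The number of events lost cannot be estimated, because the protocol gives no expected rate. The primary outcomes and the efficacy analysis are untouched. The change should be made, because uncollected events cannot be recovered, but it does not threaten the trial's main conclusion.

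The conclusion assumes that sites follow section 8 as written, and that the case report form, which is not among the documents, does not already ask about non-serious events in both arms.

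**What to change.** Reconcile sections 8 to 8.2.2 as follows:

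- In 8.1.1, define an adverse event as any untoward occurrence, related or not, in a randomised participant in either arm, from allocation to the end of follow-up. Remove the reference to a medicinal product.
- Move the six criteria to a separate definition of a serious adverse event. Use that term consistently, including in the synopsis and section 6.4.1.
- At the assessments already planned after allocation, ask one open question about untoward events, worded identically in both arms, and record the answer on the existing form.

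The cost is a rewording, one added question and slightly more data entry. No extra visits or staff are needed, and no treatment or clinical rule changes.

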## **8.2. Procedure**

### **8.2.1. AEs and SAEs**

All adverse events and serious adverse events that should be reported as defined in section 8.1.1 will be recorded in the patient's CRF.

The investigator must report SAEs to the sponsor, within 24 hours after the site has gained knowledge of the SAE. The investigator must document every SAE on the CRF. The Serious Adverse Event Report Form must be completed, signed and sent to sponsor 1. The initial report shall promptly be followed by detailed, written reports if necessary. The initial and follow-up reports shall identify the trial subjects by unique code numbers assigned to the latter.

The sponsor 1 keeps detailed records of all SAEs reported by the investigators and performs an evaluation with respect to seriousness, causality and expectedness.

